2.1.3 Safety analysis set

The safety analysis set consists of all participants who have received at least one dose of IP. Participants will be classified according to the treatment they actually received. Erroneously treated participants (eg, those randomized to treatment A but actually given treatment B) are accounted for in this analysis set by assigning them to the treatment they actually received. A participant who has on one or several occasions received active IP is classified as active.

Any deviations from the randomized treatment will be listed and considered when interpreting the safety data.

Safety, and anti-drug antibodies (ADA) data will be based on this analysis set and for whom any post-dose data are available.

2.1.4 Pharmacokinetic analysis set

This analysis set comprises all participants who received at least one dose of benralizumab and from whom PK blood samples are assumed not to be affected by factors such as protocol violations (eg, received wrong dose) and who had at least 1 quantifiable serum PK observation post first dose.

All PK summaries will be based on this analysis set.

2.1.5 OLE analysis set

This analysis set comprises all participants who start or carry on receiving at least 1 dose of benralizumab after the end of the double-blind period.

2.2 Violations and deviations

Participants who do not meet eligibility criteria but are still randomized and received at least 1 dose of IP will be analysed according to the analysis sets described in Section 2.1. There is no intention to perform a per-protocol analysis in this study.

2.2.1 Important protocol deviations

Important protocol deviations are a subset of protocol deviations that may significantly impact the completeness, accuracy, and/or reliability of the study data or that may significantly affect a participant's rights, safety, or well-being.

The final list of important protocol deviations will be documented prior to unblinding the study data (for the double-blind period) and final DBL (for the OLE period) and may include but are not be limited to the following categories:

Eligibility criteria not met (participants incorrectly randomized)

Deviations from key inclusion criteria

Deviations from key exclusion criteria

Deviations from informed consent procedures

Discontinuation criteria for IP met but participant not withdrawn from IP

Deviations from IP management and administration

Received prohibited/restricted concomitant medication

Other important protocol deviations

Scheduled study assessments not done or incorrectly performed out of visit window where the deviation is considered to have significant impact on interpretation of participant efficacy or safety data

Unblinding of treatment assignment for reasons unrelated to participant safety

Only important protocol deviations will be summarized and listed in the CSR.

Protocol deviations will be detected by means of on-site monitoring (observable protocol deviations) and programmatically derived. The process for identification and assessment will be detailed in a separate protocol deviation plan.

2.2.2 Impact on analyses due to Coronavirus Disease 2019 (COVID-19) pandemic

Given the uncertainty surrounding the future impact of the COVID-19 worldwide pandemic on clinical trials, operational procedures are being implemented in this study to maintain the integrity of collected data. Efforts will be made to collect data via alternative means where possible, when on-site visits cannot be performed.

If there is a sufficient number of protocol deviations or study disruptions as a result of COVID-19, then sensitivity analyses may be conducted to evaluate their impact on the interpretation of results. Protocol deviations, including doses or visits missed due to COVID-19 related protocol deviations will be described separately in the CSR.

COVID-19 related protocol deviations are broadly defined as follows:

Changes to visit schedules, missed visits, changes to study procedures
Discontinuation of IP or changes to the IP supply

This detail will form part of the protocol deviation plan.

During the study, confirmed or suspected cases of COVID-19 will be reported as Adverse Events (AEs) as appropriate. A listing of these cases will be produced as part of the statistical analysis.

3 PRIMARY AND SECONDARY VARIABLES

3.1 General definitions

3.1.1 Baseline definition

For efficacy, the last recorded value on or prior to the date of randomization will serve as the baseline measurement. If time is collected and relevant for the analysis, the assessment performed the same day but at a time prior to randomization will be included in the baseline definition.

For safety and PK, the last recorded value on or prior to the first dose of study treatment will serve as the baseline measurement. If time is collected, the assessment performed the same day but at a time prior to the first dose of study treatment will be included in the baseline definition.

When time of assessment is not recorded or missing, it is assumed that assessments recorded on the date of randomization (or the date of the first dose of study treatment, depending on the endpoint) were performed prior to randomization (or dosing), except in cases of protocol specified post-dose assessments. If there is no value prior to randomization (or dosing), then the baseline value will not be imputed and will be set to missing.

No data known to be collected post first dose will be used in determining the baseline value, unless otherwise specified.

For physical examinations baseline data will be collected at Visit 2 before first dose of IP.

For the Peak Pruritus Numeric Rating Scale (NRS), which is calculated as the average of daily scores over 7 days, change will be assessed by comparison to the assessments on the date

when disease control was recorded and on the 6 days after. Further details on scoring for PROs will be provided in Section [3.6.1](#).

Additional analyses for the participants who switch from placebo to benralizumab at Week 36 may be performed where the baseline value is set to the last recorded value prior to starting benralizumab (ie, likely the Week 36 measurement) to obtain an assessment of the changes occurring while receiving benralizumab.

3.1.2 Double-blind cut-off

The cut-off for data to be considered as in the double-blind period but not in the OLE is as follows:

If a participant transitions into OLE then the cut-off is the date of the first dose of OLE study treatment, ie, likely Visit 13 (Week 36), unless differently stated. If a participant does not transition into OLE then all the data will be included in the double-blind period.

For all assessments scheduled at Visit 13 (Week 36), the last recorded value on or prior to the first dose of OLE study treatment will be considered as in the double-blind period. If time is collected and relevant for the analysis, for example for PK or Biomarkers, only the assessments performed on the same day but at a time prior to the first dose of OLE study treatment will be included in the double-blind period.

When time of assessment is not recorded or missing, it is assumed that assessments recorded on the date of first dose of OLE study treatment were performed prior to dosing, except in cases of protocol specified post-dose assessments and are included in the double-blind period.

For details about how to classify AEs in the different study periods see Section [3.5.1](#).

Any data that are to be continued to be captured in the OLE period such as AEs and concomitant medications that were ongoing at the time of this cut-off shall remain as ongoing.

If an AE shows as resolved after (and including) the date of Visit 13 (Week 36) but started prior to the date of Visit 13 (Week 36) it will be shown as ongoing in the double-blind period.

A medication stopped on or before the date of Visit 13 (Week 36) (medication stop date \leq date of Visit 13) will be regarded as stopped during the double-blind period.

A medication will be regarded as ongoing at the end of the double-blind period if it started prior to the date of Visit 13 (Week 36) and was ongoing after the date of Visit 13 (Week 36).

If a medication was started and stopped on the date of Visit 13 (Week 36), it will be considered as ongoing at the end of the double-blind period.

As per Section 3.1.1, for the participants who switch from placebo to benralizumab at Visit 13 (Week 36), OLE baseline is likely to be from the double-blind period.

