Medication Procedures																					
Benralizumab or Placebo administration			X		X		X	X	X	X	X	X	X w	X b	X	X b				Section 6	

a For participants continuing in the OLE period, Visit 13 is the first treatment of the OLE period. If a participant chooses not to continue to the OLE period, the patient will be considered to have completed the study, the site will perform an EOT visit at Week 36, and the patient will return for a follow-up visit 12 weeks (+/- 7 days) after the last dose of IP, after which the participant exits the study.

b Benralizumab administration and vital signs tests will continue every 4 weeks, and urine pregnancy tests will continue every 12 weeks from Week 36 (Visit 13), during the open-label extension period until participant withdrawal or study closure.

c The IPD/EOT visit replaces the nearest regular visit: IPD/EOT visit procedures should be performed as soon as possible after the decision to discontinue IP has been made, and at the latest 4 weeks ± 7 days after the last dose of IP. For participants who discontinue IP and continue with study assessments during the double-blind treatment period, the end of treatment will be at Visit 13 (Week 36).

d The required assessments for this visit should continue to Week 72. Thereafter, they will continue at investigator's discretion.

e Investigator/delegate to record the OCS dose in the eCRF at each study visit and check compliance against participant-reported use between study visits for participants using a handheld device.

CCI

- h The AstraZeneca study physician will have the discretion to exempt participants with certain medical conditions (eg, BP lesions of the fingers/hand/neurologic condition affecting fingers/hand, visual impairment) from use of the handheld device for off-site PRO assessments. All onsite PRO assessments will however, be performed by all participants using the tablet.
- i A separate consent for the qualitative interview sub-study is required. Interviews will only be performed with consenting patients from selected countries.
- j Interview sub-study activities can only begin after the qualitative interview sub-study consent is given.

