- k Complete physical examination includes an assessment of the following: height and weight, general appearance, skin, head and neck (including eyes, ears, nose, mouth, and throat), lymph nodes, abdomen, musculoskeletal (including spine and extremities), cardiovascular, respiratory, and neurological systems.
- l Brief physical examination includes assessment of the following: weight, general appearance, skin, abdomen, cardiovascular, and respiratory system. For the brief physical examination, only information on whether the assessment was performed or not is to be recorded. Weight measurements will be performed in light clothing and without shoes and will be recorded in kilograms.
- m Testing to be conducted at local laboratory, confirmation testing to be conducted by a central laboratory.
- n A positive urine pregnancy test result must be confirmed with a serum pregnancy test.
- o Confirmatory local testing is required for those who do not have a confirmed BP diagnosis.
- p An unscheduled hematology and clinical chemistry should be performed if the visit is for relapse.
- q If not conducted in the previous 3 months.
- r Samples will be taken only at one time point, ie, at the visit when disease control has been achieved.
- s Samples will be taken at an unscheduled visit if the visit is for relapse.
- t Blood biomarkers will be collected only at one of the time points between Visits 4 and 6; ie, only at the visit that disease control has been achieved and before steroid taper is commenced.
- u Skin biopsies will be taken from peri-lesional skin for histopathology and CCI [REDACTED] research.
- v For participants without a confirmed diagnosis, no biopsy for CCI [REDACTED] is collected. In these participants, the biopsy will be for inclusion criteria confirmation at the local lab and immunohistochemistry for exploratory research.
- w Benralizumab administration only; for participants who continue the study in the open-label extension.

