As supportive analyses to explore the timing of relapse events, the time to first BP relapse will also be analyzed, where time to first relapse is defined as the earliest time after randomization that any of the relapse criteria are met. This analysis will use a log-rank test stratified by baseline disease severity (moderate; severe) and time of BP diagnosis (ie, participants with newly diagnosed BP versus participants with a previous diagnosis of BP who have relapsed). A p-value, corresponding to a 2-sided test, will be presented to compare the benralizumab and placebo treatment groups. A Cox-proportional hazards model will be used to estimate the hazard ratio and its 95% CI. The median time to first relapse will be estimated from the Kaplan-Meier curves for the benralizumab and placebo treatment groups.

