3.2 Primary outcome variable

The primary outcome variable is a binary response whereby participants will be classified as responders if they are in complete remission while off OCS for ≥ 2 months at Week 36. Otherwise, participants will be classified as non-responders.

Investigators will be asked to make a clinical assessment of the participants to determine their BP disease state (ie, active disease, disease control, end of consolidation phase, remission, and relapse) from Visit 2 until the end of the double-blind period, during the OLE period, and then in addition at the IP Discontinuation (IPD), End of Treatment (EOT) and follow-up visit.

At each visit, Investigators will be required to assess a participant's outcome measures, including the states defined in Table 4. The outcome measure will be documented in the eCRF.

Table 4 Definitions for Bullous Pemphigoid Outcome Measures

Outcome measure	Definition ^b
Disease control/beginning of consolidation phase	The time at which new lesions cease to form and established lesions begin to heal or pruritic symptoms start to abate
End of consolidation phase	Time at which no new lesions have developed for a minimum of 2 weeks and approximately 80% of lesions have healed and pruritic symptoms are minimal
Sustained partial remission on minimal steroid ^a /off steroid therapy	The presence of transient new lesions that heal within 1 week while the participant is on minimal steroid therapy or off steroid therapy for at least 2 months
Sustained complete remission on minimal steroid ^a /off steroid therapy	The absence of new or established lesions or pruritus while the participant is on minimal steroid therapy/off steroid therapy for at least 2 months
Relapse	The appearance of 3 or more new lesions per month (blisters, eczematous lesions, or urticarial plaques) or at least one large (> 10 cm diameter) eczematous lesion or urticarial plaques that do not heal within 1 week, or the extension of established lesions or daily pruritus in participants who have achieved disease control

^b Minimal steroid therapy is defined as less than or equal to 0.1 mg/kg/day of prednisone or equivalent

^c Definitions as per [Murrell et al 2012](#)

Each BP disease state clinical assessment collected during any scheduled/ unscheduled/ IPD/ EOT/ follow-up visits will be included in the Week 36 visit as per adjusted defined visit window, see Section [3.1.4](#), and analysed accordingly.

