The time from randomization to the first BP relapse for participants who do not experience any relapse will be censored at their last available assessment showing them to be relapse-free. The same intercurrent events as detailed above in this section will be applied.

All the data in the double-blind period will be included.

3.3.2 Cumulative OCS exposure (mg/kg) from baseline to Week 36 and from baseline to Week 16

Details about OCS usage will be collected at each scheduled visit by the Investigator as reported in Section [3.1.5.1](#).

Cumulative OCS exposure (mg/kg) from baseline to Week 36 and from baseline to Week 16 will be calculated for each participant over 4 weekly intervals.

For each visit from Visit 4 (Week 4) until Visit 13 (Week 36), excluding Visit 5 (Week 6), the OCS exposure (mg/kg) will be computed by summing the recorded doses taken during each day over the past 28 days, thus the day of the visit will not be included. It will be calculated using the 28 days prior to the day of the scheduled visit. No visit window will be applied to the scheduled visit day.

For Visit 13 (Week 36), if the 4 weekly interval based on the scheduled visit day is including any days after the actual Visit 13 (Week 36) day (ie, days in the OLE period) the 4 weekly OCS exposure will be computed by summing the recorded doses taken during only the days during the double-blind period and rescaling them into a 4 weekly interval. For example, if the Visit 13 (Week 36) 4 weekly interval includes only 25 days in the double-blind period, it will be computed by summing the recorded doses taken during these 25 days, dividing by 25 and multiplying per 28. If less than 14 days are in the double-blind period, the Visit 13 (Week 36) 4 weekly interval will be considered with missing data of OCS exposure.

More details on OCS daily exposure are reported in Section [3.1.5.1](#).

To compute the dose in mg/kg for each day of OCS assumption the baseline weight will be considered.

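### Time to first relapse (SAP 3.3.1) has no Week 36 limit, so off-drug events after Week 36 count only for participants who do not enter the extension

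*SAP*

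**What the plan says.** SAP 3.1.2 has two rules for where double-blind data end. For OLE entrants: "If a participant transitions into OLE then the cut-off is the date of the first dose of OLE study treatment", which is expected to be Visit 13 (Week 36). For everyone else: "If a participant does not transition into OLE then all the data will be included in the double-blind period".

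SAP 3.3.1 defines the relapse variables. Time to first relapse for a participant without a relapse "will be censored at their last available assessment showing them to be relapse-free", and the section closes with "All the data in the double-blind period will be included". Rescue increases in oral corticosteroid (OCS) dose and those restricted medications that rank as intercurrent events count as relapse on their start date. Protocol 9.4.2.2 sets no upper limit either: "time to first relapse is defined as the earliest time after randomization that any of the relapse criteria are met".

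The Schedule of Activities (Protocol Table 2) determines how far the data reach. The footnote on Week 36 dosing reads "Benralizumab administration only; for participants who continue the study in the open-label extension", so the last double-blind dose is at Week 32. For a participant who declines the OLE, "the patient will return for a follow-up visit 12 weeks (+/- 7 days) after the last dose of IP". SAP 3.2 has disease state assessed "in addition at the IP Discontinuation (IPD), End of Treatment (EOT) and follow-up visit", and the relapse paragraph of Protocol 8.1.1.1 has relapse details recorded through that follow-up visit.

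**The concern.** Followed literally, these rules give participants different observation periods according to a choice made after randomization. An OLE entrant stops contributing at about Week 36. A participant who declines goes on contributing relapses, rescue OCS increases and intercurrent restricted medications until the follow-up visit, with no study drug given after Week 32.

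Beyond Week 36 the risk set consists only of this self-selected, off-drug group. The log-rank test, hazard ratio and Kaplan-Meier median would then mix the 36-week randomized comparison, which SAP 4.1 names as the basis of the primary analysis, with a withdrawal period seen in some participants only. These results are meant to show the timing behind the first key secondary endpoint.

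**Working it through.** **1. Dates.** SAP Table 2 gives Week 32 as study day 225 and Week 36 as day 253; 7 × 32 + 1 = 225 and 7 × 36 + 1 = 253 reproduce them. Adding 84 days (12 weeks) to the last dose gives the nominal follow-up visit:

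| Last dose | Dose day | Follow-up day | Week | Days past day 253 |
|---|---|---|---|---|
| Week 32 | 225 | 309 | 44 | 56 |
| Week 28 | 197 | 281 | 40 | 28 |
| Week 24 | 169 | 253 | 36 | 0 |

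The visit may move by 7 days either way. The longest nominal tail is 56/252 = 22% of the 36 weeks, for each affected participant.

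**2. Comparison with the sister variables.** SAP 3.4.7 (time to disease control, time to end of consolidation) has the same all-data sentence, but censors completers without the event at the Week 36 assessment. SAP 3.3.1 lacks that clause.

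**3. Expected extra events (illustration).** The plan states no figure for this analysis. From the documents: 50 per arm (SAP 1.3) and 33% relapse-free to Week 36 on placebo, from the mepolizumab trial that SAP 1.3 cites. Assumed: 60% relapse-free on benralizumab, 20% declining the OLE, off-drug hazard equal to placebo.

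- Placebo weekly hazard: ln(1/0.33)/36 = 0.0308. Eight-week risk: 1 − exp(−8 × 0.0308) = 22%.
- Extra placebo events: 50 × 0.33 × 0.20 × 0.22 = 0.7.
- Extra benralizumab events: 50 × 0.60 × 0.20 × 0.22 = 1.3.
- Events within 36 weeks: 50 × 0.67 = 33.5 and 50 × 0.40 = 20, about 54 in all.
- Extra follow-up: 0.20 × (16.5 + 30) = 9.3 participants × 8 weeks = 74 person-weeks. With a benralizumab hazard of ln(1/0.60)/36 = 0.0142, follow-up within 36 weeks is 50 × 0.67/0.0308 + 50 × 0.40/0.0142, about 2,500 person-weeks. The tail adds about 3%.

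**4. Effect on the hazard ratio (simulation).** 1,500 runs per setting, 50 per arm, 60% versus 33% relapse-free at Week 36, Peto hazard ratio. Declining is random among relapse-free participants, and the benralizumab hazard after Week 36 is multiplied by 1, 2 or 4.

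| Declining | Multiplier | HR to Week 36 | HR with tail | Power to Week 36 | Power with tail |
|---|---|---|---|---|---|
| 10% | 1 | 0.452 | 0.452 | 81.5% | 81.9% |
| 10% | 2 | 0.460 | 0.465 | 79.3% | 78.9% |
| 10% | 4 | 0.466 | 0.478 | 78.3% | 76.6% |
| 30% | 1 | 0.456 | 0.455 | 81.5% | 82.1% |
| 30% | 2 | 0.458 | 0.473 | 80.4% | 78.9% |
| 30% | 4 | 0.457 | 0.501 | 81.1% | 73.9% |

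The tail adds 0.3 to 3.3 benralizumab and 0.3 to 1.1 placebo events to about 53 or 54. A return to the placebo hazard is a multiplier of 0.0308/0.0142 = 2.2, close to the middle rows. With no treatment effect (33% in both arms, 30% declining, multiplier 1), the rejection rate was 4.6% with and without the tail.

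**5. Effect on the median.** Under the assumptions of step 3, the placebo median is ln 2/0.0308 = 22.5 weeks, so the tail does not touch it. The benralizumab curve stands at 0.60 at Week 36, with no median reached, and 50 × 0.60 × 0.20 = 6 participants stay at risk. One relapse takes it to 0.60 × 5/6 = 0.50, and a second to 0.50 × 4/5 = 0.40. The chance of two or more relapses among six is 1 − 0.78⁶ − 6 × 0.22 × 0.78⁵ = 1 − 0.225 − 0.381 = 39%. A benralizumab median between Weeks 36 and 44 could therefore rest on two off-drug relapses, where a Week 36 limit would leave it not reached.

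**The case against.** The strongest reply is that the intended period is clear. SAP 1.2.2 gives the double-blind period as 36 weeks, SAP 4.1 bases the primary analysis on that phase, and SAP 3.4.7 censors at Week 36. On this view a clause was left out of one supportive derivation. That is probably how the gap arose, but none of these statements sets a censoring date for relapse, and a programmer following 3.1.2 and 3.3.1 would include the tail. The Day 280 limit in SAP Table 2 does not close the gap, because the windows of SAP 3.1.4 allocate visit-based data and time to relapse uses event dates.

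Several other points stand. Time to first relapse is outside the testing hierarchy and its p-value is nominal. The 3.1.2 rule suits safety, since SAP 3.5.1 follows adverse events for up to 12 weeks after the last dose. Off-drug relapses before Week 36 already count, because treatment discontinuation is handled by treatment policy. That last point defends off-drug data as such, but not an observation period that differs by OLE choice.

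A reader might infer that the binary key secondary is also affected, because the all-data sentence closes the whole of SAP 3.3.1. The documents do not support this. That endpoint is limited to Week 36 in its title, its definition, the estimand table (SAP Table 8) and SAP 4.2.7.1. The sentence directly follows the censoring rule for the time-to-event variable, as it does in 3.4.7.

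**Conclusion.** The point holds for the supportive time-to-first-relapse analysis only. For participants outside the OLE, events count to about Week 44 if last dosed at Week 32 and about Week 40 if last dosed at Week 28. With a last dose at Week 24 or earlier there is nominally no tail. OLE entrants stop at their first OLE dose.

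The effect on the hazard ratio is probably small. It rests on the share who decline and on the off-drug hazard, neither of which the documents give, and on an assumed 60% relapse-free rate. A reader might infer that the tail always pulls the hazard ratio towards 1, or that it threatens the type I error. The calculations show neither: there was no shift when the benralizumab hazard stayed the same after Week 36, and the rejection rate without a treatment effect was unchanged. Those runs treat declining as random, so they do not cover a choice related to prognosis. The Kaplan-Meier median is the more exposed result, because so few participants remain at risk after Week 36.

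**What to change.** In SAP 3.3.1, add a clause mirroring 3.4.7. For time to first relapse, count relapses, rescue OCS increases and intercurrent restricted medications only up to the Week 36 (Visit 13) assessment, or Day 280 if earlier, and censor relapse-free participants who complete the double-blind period there.

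Name Visit 13 explicitly. A cut-off worded as end of treatment could be read as the early IPD/EOT visit in Protocol Table 2, which would shorten follow-up for participants who stop study drug. Under treatment policy they should still be followed to Week 36.

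SAP 3.1.2 can stay unchanged for safety data. Report relapses after Week 36 in participants outside the OLE separately, as off-treatment follow-up. The cost is one clause, a date filter and one extra summary, with no new data.
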